### **9.4 Data Monitoring**

Data safety and monitoring procedures will be in place before enrollment begins and monitoring will be performed on a regular basis throughout the subject accrual and treatment periods.

#### **9.4.1 Data and Safety Monitoring Team**

The data and safety monitoring team was discussed and approved by the NINDS staff. It will comprise the local IRB, the trial's safety compliance officer (SCO) (Section 10.3.2), and an IMSM from outside the study and data management institutions, assisted by two external medical safety consultants with expertise in CCM disease and in statin therapy respectively. The data and safety monitoring team will provide an ongoing review

of the research, adjudicating adverse events, performing interim safety and efficacy analyses, and assessing progress towards achieving the goals of the study.

Safety assessment will take place at the end of the first year, after 30 participants have completed 12 months of follow-up and again after 60 subjects have completed 12 months of follow-up. Additional reviews will be decided on an ad hoc basis based on the frequency of safety endpoints encountered during the trial. The Brain Injury Outcomes (BIOS) statistician will provide the IMSM and the PI relevant tables including information regarding demographics, rebleeding rates, AEs, SAEs, and radiological and laboratory abnormalities (CT scans, liver function, etc.), per treatment assignments labeled A and B without unblinding. In addition, the IMSM will be provided with a copy of the SAE forms received. Further information will be given to the IMSM upon his/her request. The IMSM will provide written recommendation as to whether the study may continue, possible amendment(s) to the protocol, or whether the study should be stopped. The final decision will rest with the study PI, guided by protocol mandated safety thresholds to suspend and potentially revise or stop the trial (see below). Any protocol revision would require approval by the IRB, and shall be discussed with NINDS staff and external consultants prior to implementation.

#### **9.4.2 Safety Threshold**

While the proposed trial is underpowered to detect a significant difference in symptomatic clinical rebleeding rates between groups, **differential and absolute rates of hemorrhage in the placebo and treatment cohorts will be critically analyzed throughout the trial**. Continuous monitoring will be initiated with the enrollment of the tenth subject in the study. A symptomatic brain hemorrhage from the index hemorrhagic CA lesion or another source will be considered a safety endpoint for the respective subject. The natural history of untreated brainstem CA demonstrates a 32.1% (CI 1-59%) bleeding risk within two years after prior hemorrhage (18), and our own pilot data of 14 trial candidates undergoing biomarker studies showed 4 symptomatic rebleeds (28%) during 21 patient-years of follow-up (Figure 7). We will hence decide to implement a running safety threshold to preemptively suspend trial enrollment for a full safety review **if at any time, >40% of subjects in the treatment group suffer a symptomatic brain hemorrhage from the index CCM lesion or another source**. Subclinical bleeding is likely more common, and the proposed trial is designed and powered to identify increased sub-clinical iron leak in CCM lesions using our validated QSM biomarker, in addition to careful monitoring of clinically overt hemorrhages.

### **9.5 Data analysis**

Exploratory analyses for quality assurance and understanding of missing data patterns and distributions will be performed on the outcomes and all measurements to be used in the primary and secondary analyses. For the **primary aim**, a linear mixed model will be used that adjusts for gender to evaluate the difference between the two arms in the QSM change of the index hemorrhagic lesion per patient. Adjustment for gender is necessary because the patients will be randomized by gender stratification. Not control-

ling for stratification variables can lead to upwardly biased standard errors and a decreased power (116). The model accounts for within-patient correlation between the measurements (117, 118). Patients with outcome measurements in both periods will be included in the initial intention-to-treat analysis. A secondary analysis of the percent QSM change per year shall be conducted per treatment rendered for all patients with at least one annual epoch of measurements. Significance levels are assumed as per sample size calculations.

To address **secondary aims**, each of the other outcomes will be analyzed with a similar approach, first per intention-to-treat sample in patients receiving two annual epochs of follow-up, and second by treatment-rendered in all patients with at least one annual epoch of measurements. To assess the difference in level of DCEQP permeability in lesion and brain between the two arms, a linear mixed model adjusted for gender as described for QSM will be used to evaluate the difference in percent change per year in lesional and WMF permeability. A similar adjusted linear logistic mixed model for the binary outcomes will be used to evaluate the difference between the two arms in the rates of symptomatic hemorrhage (per adjudicated definition), lesion expansion, and “biomarker event” (increase in QSM during an epoch above the pre-defined 6% threshold). To assess the difference of event rates for adverse events (AEs) per patient, an adjusted Poisson linear mixed model controlling for gender will be used to regress count outcomes in order to evaluate the difference in AE event rates between the two treatment arms. The AEs will be assigned preferred terms per body systems according to the Medical Dictionary for Drug Regulatory Affairs (MEDDRA) classification of the WHO terminology. AEs (categorized by body system) and abnormal laboratory data will be summarized and compared by treatment group. The compliance rate, general attrition rate and the attrition rate due to adverse events between the two groups shall also be compared. For analysis of leukocyte ROCK activity and functional outcomes (mRS, Euro QOL 5D and VAS, Neuro QOL Communication, and mini-MS score), an adjusted linear mixed model will be used to evaluate the difference in respective outcome score change per year between the two arms. We will report point-estimates, confidence intervals, and p-values for each analysis.

Demographic and baseline data, including age, gender, ethnicity, age at symptom onset, number of prior hemorrhagic events, number of T2-weighted lesions, number of susceptibility weighted imaging (SWI) lesions, etc., will be summarized. As a secondary model, a linear mixed model that adjusts for those baseline factors shown to be associated with the outcome will be created, and will consider the constraints of a small numbers in the respective sub-cohorts. Presenting the mean, standard deviation, median, minimum and maximum with the total number of patients contributing values, will summarize continuous endpoints. Presenting the frequency or proportion of patients in each category will summarize categorical endpoints. For all analyses, biased effects in three prespecified subgroups shall be queried (male/female, sporadic/familial genotype, and brain-stem/other lesion location). If the numbers of genotyped subjects allow, we will also compare treatment effect in different genotypes among familial cases. Similar analyses were recently performed by our team in the MISTIE II and CLEAR III trials (113, 114).

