**6.2.6 Fifteen, 18, and 21 month follow-up phone call (V6, V7, and V8)**

The 15, 18, and 21 month visits will consist of a phone call from the Trial Nurse or coordinator to collect the following information:

- Modified Rankin score (mRS)
- Concomitant medications
- Adverse events

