## 8. CRITERIA FOR INTERVENTION DISCONTINUATION

Atorvastatin/Placebo administration will be discontinued for any of the following reasons (designated as serious AEs or Category C in the preceding Table 2):

- Symptomatic intracerebral hemorrhage (ICH) whether primary, arising from index cavernous malformation that previously bled, or in other lesion, or other ICH of any kind
- Severe allergic reaction
- Rhabdomyolysis
- Markedly elevated liver enzymes
- Liver failure
- Pancreatitis
- Pregnancy
- Intolerable adverse events that persist or recur after serial dose reduction.
- In the investigator's judgment, withdrawal from the trial would be in the subject's best interest (Drug interaction/glycemic control).
- The subject or legal representative withdraws consent, or patient undergoes surgical resection or irradiation of CCM lesion, other brain surgery or irradiation for any cause.
- Patient develops clinical indications for statin use for cholesterol or cardiovascular indications unrelated to CCM.

If one or more of these events occur after commencing the study drug, the subject will be considered to have reached a safety endpoint. Study drug or placebo shall be discontinued. All subjects reaching safety endpoints will be followed through the 24-month follow up visit as a part of the outcome assessment for the study. An attempt will be made to contact subjects who withdraw from the study or who are lost to follow up for safety evaluation. If these subjects wish not to cooperate there will be no additional follow up.

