### **9.3.2 Potential Missing Data, Attrition and Premature Trial Endpoint**

We considered all potential causes of missing data and we developed strategies to minimize and mitigate them. In initial pilot studies, 34 of 177 (19%) QSM assessments in CA patients were unusable due to technical reasons (mostly patient movement during image acquisition). We eliminated this problem in the most recent 25 consecutive cases with specific patient instructions. We now implement a further step of reviewing the QSM acquisition, and rapidly processing it (10 minutes on local Matlab computer terminals in our laboratory). This allows us to repeat the QSM acquisition if needed, before proceeding with contrast injection for DCEQP measurements. This “chaperoned biomarker acquisition” reduces to virtually zero the rate of missing QSM measures (See letter by [name] and Protocol Section 6.5). We nevertheless project up to 10% missing biomarker data related to imaging (claustrophobia, etc.). We further project an additional 10% missing data due to imperfect follow-up, higher than that recorded in recent trials conducted by our teams (113, 114).

Up to 20% of subjects randomized to atorvastatin (10% of trial subjects) might not tolerate the 80 mg/day dose. Many will continue the drug at the lower dose. In fact, **serious side effects or intolerance of the lower dose are expected to result in attrition in less than 5% of cases**, per extensive meta-analyses of trial experience with the study drug (See Protection of Human Subjects; and Protocol section 7.3). Another **20-30% of cases might reach a prespecified study endpoint** because of SH, and they would also stop the drug before the end of the 2-years follow-up. All subjects who stop the drug, and those with non-compliance as defined, will still be followed for the full 2 years with scheduled clinical and imaging assessments, and will be included in the **primary analysis per intention-to-treat**.

To permit secondary analysis per treatment rendered, at the power and Type I error described above, we decided to **expand the sample size by an ample 37.5%, factoring the highest combined estimates of missing data and attrition.**

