## Imputation of Missing Outcomes Data, and Sensitivity Analyses

As mentioned above, every effort will be made to minimize the number of patients will missing outcome measures. However, despite these best efforts, it is likely that some missing outcome data will be present in this data set. In order to account for these missing outcome values, we will perform a sensitivity analyses that uses a Markov chain Monte Carlo (MCMC) model to impute several possible measures for patients missing the primary outcome.

With multiple imputation (MI), we assume that the missing data points are missing at random (MAR) (119). We will use those baseline demographic variables, which are strongly associated with clinical outcome, to improve the missing outcome imputations. We will then generate an iteration series plot and autocorrelation function (ACF) plot for MCMC simulation. We shall plan 20 imputations with a 98% relative efficiency to accommodate a worst-case scenario, where 37.5% of the outcomes data points are missing (120). To verify if the missing data points occur at random we will utilize a tipping-point approach (121) that will follow MI procedure for sensitivity analysis and estimation of the MI departure from the MAR assumption. We shall use the sensitivity analysis to recalculate efficacy estimates from regression models described in the data analysis of the primary and secondary outcomes. This will help determine how sensitive efficacy estimates are under different assumed distributions for missing outcomes data. In other words, the results obtained by imputing missing data with several plausible outcomes will give a range of possible treatment effects under different assumptions of missingness.

We will have greater confidence in efficacy estimates if we obtain clinically and statistically significant results under the worst-case scenarios from the sensitivity analyses (e.g. imputing no improvement in the QSM change scores for all patients with missing data in the active treatment arm). In contrast, greater caution should be given to estimates of efficacy if results obtained from regression analyses are no longer clinically and statistically significant under extreme scenarios for the missing data. SAS 9.4 (SAS Institute Inc., Cary, NC, USA) will be used for MI and sensitivity analysis.

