### **Analysis of Treatment Compliance**

Treatment compliance is crucial to validate the study objectives. A compliance threshold of 90% will be implemented for proposed analyses per treatment rendered. Drug adherence will be rigorously monitored through an innovative electronic system that will provide continuously streamed real time data in addition to confirmatory manual pill count at each follow up call and scheduled visits. Assessment of compliance is an integral component at every scheduled or unscheduled evaluation and will be based on the **electronically acquired data as well as the missed doses log in the case report form (CRF)**. *A subject will be deemed noncompliant with the study intervention if he/she misses more than 21 consecutive doses at any point, or accumulate a log of 75 missed doses throughout the study.* Treatment compliance shall be compared in atorvastatin versus placebo cases as one of the secondary aims of the study.

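### The first, nominally intention-to-treat hemorrhage comparison keeps only subjects with two annual epochs of follow-up, so an observed year-1 bleed is dropped when the second year is missing (minor)

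*Combined protocol and SAP*

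**What the plan says.** Section 9.5 gives one rule for all secondary outcomes, in two steps: "first per intention-to-treat sample in patients receiving two annual epochs of follow-up, and second by treatment-rendered". The later step takes anyone who has one annual epoch or more. Hemorrhage falls under this rule. Of the sex-adjusted logistic mixed model, the text says that it "will be used to evaluate the difference between the two arms in the rates of symptomatic hemorrhage (per adjudicated definition), lesion expansion"; QSM threshold increases are covered too. For the second analysis, the subsection Analysis of Treatment Compliance adds: "A compliance threshold of 90% will be implemented for proposed analyses per treatment rendered".

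On follow-up, Section 9.3.2 says that subjects who stop the drug "will still be followed for the full 2 years with scheduled clinical and imaging assessments". Sections 7.3.1 and 8 say the same of subjects who stop because of a bleed. Section 9.3.2 also expects losses: "We further project an additional 10% missing data due to imperfect follow-up". Section 8 says of subjects who withdraw or are lost: "If these subjects wish not to cooperate there will be no additional follow up".

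The imputation subsection of 9.5 plans a sensitivity analysis "to impute several possible measures for patients missing the primary outcome". It adds that this analysis will be used to re-estimate effects from the regression models for both primary and secondary outcomes.

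Section 9.2 defines the hemorrhage outcome as clinically overt bleeding in the index lesion, by adjudicated criteria.

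**The concern.** A two-epoch requirement has some logic for the QSM change score, which needs paired scans. It has little for a bleed. A hemorrhage at month 5 is known whether or not the subject is seen again, and it does not need a visit to be recorded. Section 6.2.6, for example, states: "The 15, 18, and 21 month visits will consist of a phone call from the Trial Nurse or coordinator". These calls collect adverse events, and Section 10.4.2 has each event recorded with its start and end dates.

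The rule also selects subjects on something that happens after randomization and that the bleed itself may influence, through disability, withdrawal or death. Rebleeding is the clinical event that QSM stands in for, and Section 9.5 promises a point estimate, confidence interval and p-value for it. With few events expected per arm, each dropped bleed carries weight. Section 9.5 contains no hemorrhage comparison in all randomized subjects by assigned arm.

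**Working it through.** **The plan's own figure.** The documents give no sample size for hemorrhage. The 40 per arm comes from the QSM outcome. With SD 30, two measurements and correlation 0, the SD of the two-year mean is 30 × √(1/2) = 21.2. A 20-point difference at two-sided 0.05 and 90% power then needs 25 per arm (noncentral t, power 0.904), and 25 / (1 − 0.375) = 40. This reproduces Section 9.3.1.

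**Inputs for hemorrhage.**
- 40 per arm (9.3.1).
- Two-year bleeding risk 32.1% (9.4.2). This is for untreated brainstem lesions, CI 1-59%. The trial is not limited to brainstem lesions, so it is an illustration.
- A 20-30% share reaching the hemorrhage endpoint (9.3.2). The low end, 20%, is used as a second case.
- Share m of all other subjects lacking year 2: 10%. Section 9.3.2 gives 10% as missing data from imperfect follow-up. Reading it as the share without a second year is an inference.
- Share d of year-1 bleeders lacking year 2: not given. Assumed 10%, 25% or 50%.
- Constant hazard over the two years: assumed.

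**Formulas.** Annual risk p = 1 − √(1 − two-year risk). Year-1 bleeders = 40p. First bleeds in year 2 = 40(1 − p)p. Dropped year-1 bleeds = 40pd. Proportion seen in two-epoch subjects = [p(1 − d) + (1 − p)p(1 − m)] / [p(1 − d) + (1 − p)(1 − m)].

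**At 32.1%.** p = 1 − √0.679 = 0.176. Year-1 bleeders: 7.04 per arm. Year-2 first bleeds: 5.80. Subjects without a year-1 bleed who keep year 2: 32.96 × 0.9 = 29.66, of whom 5.80 × 0.9 = 5.22 bleed.

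| d | Bleeds dropped per arm | Proportion seen |
|---|---|---|
| 10% | 0.7 | (6.34 + 5.22) / (6.34 + 29.66) = 32.1% |
| 25% | 1.8 | (5.28 + 5.22) / (5.28 + 29.66) = 30.0% |
| 50% | 3.5 | (3.52 + 5.22) / (3.52 + 29.66) = 26.3% |

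**At 20%.** p = 0.106, with 4.2 year-1 bleeders per arm. Bleeds dropped: 0.4, 1.1 or 2.1. Proportion seen: 20.0%, 18.6% or 16.1%.

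**Loss that differs by arm, at 32.1%.** With equal true risk and bleeder loss of 10% in one arm and 50% in the other, the gap is 32.1 − 26.3 = 5.8 points, all of it false. The reverse can also happen. Suppose the annual risk in one arm is halved to 8.8%, so its two-year risk is 1 − 0.912² = 16.8%, and bleeder loss is 10% there and 50% in the other arm. The true 15.3-point difference then reads 26.3 − 16.8 = 9.5.

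**Scale.** The standard error of a difference at 40 per arm and 32.1% is √(2 × 0.321 × 0.679 / 40) = 10.4 points, so 5.8 points is about 0.6 of a standard error.

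**The case against.** The strongest reply is that the plan keeps bleeders in follow-up, and that its only documented follow-up loss, 10%, causes no distortion when it falls equally on bleeders and others. That stands. Every shifted proportion above rests on a bleeder loss that the documents do not give, and the false gap also needs that loss to differ by arm.

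A second reply is that imputation covers the gap. A subject without a second-year QSM is missing the primary outcome, the secondary models are to be re-estimated, and multiple imputation normally leaves observed values alone. This is a possible route back for such subjects. It remains a sensitivity analysis tied to a missing primary outcome, with no stated rule that an observed bleed is kept.

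Third, bleeds are reported elsewhere: in the A/B monitoring tables (9.4.1), in the running safety threshold (9.4.2) and among the adverse events compared by group (9.5). A reader might infer that dropped bleeds vanish from the trial. They do not. None of these, however, is the adjudicated comparison in all randomized subjects.

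A reader might also infer that the 90% compliance threshold shuts bleeders out of the second analysis. The documents do not establish that. Noncompliance is defined by missed doses, and a protocol-mandated stop after a bleed is not said to count as missed doses. A bleeder with one completed epoch may enter that analysis. Only a bleeder with none is clearly outside both.

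**Conclusion.** The point holds as a minor one. Followed as written, Section 9.5 removes some observed bleeds from its only assigned-arm hemorrhage comparison. The expected number is small: about 0.7 per arm at 32.1% two-year risk and 10% equal loss, with no change in the proportion. Bias arises only under unequal loss, and 26.3% and 5.8 points illustrate an assumed 50% loss among year-1 bleeders. All figures assume constant hazard and 10% loss among other subjects.

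A reader might go further and call the hemorrhage result biased, or infer that bleeders as a group are excluded. The documents support neither, because bleeders are scheduled through month 24 and no differential loss is projected. Nor is power the argument: Section 9.4.2 already says that the trial is underpowered for rebleeding, and that stays true under either analysis. Keeping a bleeder's off-drug year in the assigned arm is intended and is not a fault. The safety threshold above 40% counts subjects and is unaffected.

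**What to change.** In Section 9.5, make the main hemorrhage comparison the first adjudicated symptomatic hemorrhage in the index lesion (the 9.2 definition) from randomization to 24 months. Use all randomized subjects by assigned arm, adjust for sex, and count every observed bleed whether or not a second year exists. Report hemorrhage from any lesion alongside.

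A subject-level 24-month comparison or a time-to-first-bleed model with censoring at last contact would both serve; the choice between them is a preference. Keep the two-epoch logistic mixed model as a sensitivity analysis, and say what counts as an epoch of follow-up for hemorrhage.

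The cost is wording and one standard model on dates already collected, with no new visits or subjects. The downside is that repeat bleeds in the same subject are only listed descriptively.

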We recently reported the first prospective assessment of QSM during longitudinal follow-up of human CCM subjects, and correlated paired QSM assessments during 1-year epochs with new clinical events (58). Among cases without recent bleeding or lesion growth within a year of the first measurement, CCM lesions that remained stable during longitudinal follow-up had a tiny average decrease (-3.2%) in mean lesional QSM. CCMs with demonstrated growth or symptomatic bleeding exhibited a significant increase (+44%) in mean lesional QSM (Figure 6). Receiver operating curves (ROC) of QSM change in individual subjects demonstrated a sensitivity of 82.29% and specificity of 88.89% at a +5.81% threshold change, highly significant ( $p = 0.0004$ ), with a mere **+5.81% QSM change. These results link a robust QSM change directly to clinical events, and define a threshold QSM change as a sensitive and specific biomarker event.**

**QSM change and clinical events in CAs after recent Symptomatic Hemorrhage.** In further pilot studies, we assessed lesional QSM change during prospective **follow-up of a pilot cohort of CA patients with a clinical bleed within the prior year (meeting the proposed trial criteria)** (59).

Sixteen subjects followed for 1 or 2 years (total 22 person-year epochs), underwent paired QSM assessments at the beginning and end of each person-year epoch. Mean QSM in the index CA hemorrhagic lesion increased by an average of +7.93% per person-

[figure not shown]

year epoch in the full cohort. Closer examination revealed 10/22 epochs with a documented threshold biomarker event ( $\geq 6\%$  QSM increase). This was twice as frequent as clinical events. No clinical event occurred without a threshold increase in QSM (Figure 7). A primary aim of the proposed trial shall explore whether the change in QSM is altered by statin treatment. A secondary aim shall explore the relationship of QSM change to clinical events in statin and placebo treated subjects.

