#### Dynamic Contrast-Enhanced Quantitative Perfusion (DCEQP)

[figure not shown]
**Figure 9:** Multi-echo T2\*-weighted images cover the whole brain and are used to quantify magnetic susceptibility in cavernous angiomas.

The DCEQP protocol consists of 3 components that are run in sequence: (1) Arterial Input Function (AIF) Localizer (2) T1-weighted map and (3) Contrast Enhanced DCE dynamic scan.

Arterial Input Function (AIF) Localizer: A 3D Time-of-Flight acquired at the level of the lower brainstem and pons to cover the internal carotid arteries (Figure 10, yellow box). The reconstructed maximum intensity projection (MIP) images in both the coronal and sagittal views will be used to prescribe the slice to locating the artery for the AIF.

After the AIF localizer is acquired to image the position and angulation of the internal carotid arteries, a saturation recovery gradient recalled sequence (SPGR) will be acquired both for an initial T1-weighted measurement and for the subsequent dynamic imaging (Figure 11). The prototypical acquisition parameters will be: echo time TE = 1.9 ms, repetition time TR = 3.9 ms, flip angle = 30°, field of view = 230 x 182 mm^2, slice thickness = 8 mm, matrix size = 96x61, SENSE factor = 2, centric order phase encoding. The same base sequence is used for both the T1-weighted mapping and the dynamic series part. The base sequence consists of two imaging slabs (stacks):

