#### Image Post-Processing

All post-imaging processing will be completed locally at the MRIC using an existing image reconstruction pipeline on a computer running MATLAB software (Mathworks, Natick, MA). QSM images will be reconstructed by using a morphology-enabled dipole inversion algorithm (98), which generates the local susceptibility distribution by inverting the estimated tissue field map with prior information from the magnitude images. The tissue field map will be obtained by removing the background field induced by large susceptibility sources (i.e. air/tissue interface) from the field map derived from the gradient-echo phase images (60). Mean lesional susceptibility values will be generated by drawing a region of interest (ROI) around the lesion on the resulting QSM image in ImageJ for each slice in which the lesion is visible, then averaging all pixels within the ROIs for a lesion.

Final permeability values will be calculated in MATLAB by applying the Patlak method voxel-wise, represented by the following equation:  $\frac{C_t(t)}{C_{a(t)}} = K_i \frac{\int_0^t C_a(\tau) d\tau}{C_{a(t)}} + V_b$ , where each  $C_t(t)$  is the concentration time-course of each voxel of tissue. The unidirectional influx constant,  $K_i$ , is estimated as the slope of the Patlak plot created by the above equation. This equation becomes valid after some time as the vascular phase vanishes, and data points from the first third of each time course are not included for this estimation. More detailed discussions of the methodology have been published (60).

Lesional permeability values will be generated similarly to QSM. For DCEQP studies, in addition to the lesion of interest, ROIs will be taken for either the choroid plexus (if covered by the imaging stack) or normal-appearing white matter far ( $> 5$  mm) from the lesion, to be used as an internal reference value at follow up. Permeability values for White Matter Far (WMF) shall be generated in regions of interest (ROI) covering 3.6 X 3.6 mm (16 pixels or approximately 12.9 mm^2/ROI based on 256-256 matrix for axial brain MR slices). WMF regions are chosen in brain devoid of CA lesions on any MR sequence, as far as possible from and always  $>16$  mm from the border of a visualized lesion, including the tiny SWI lesions.

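### Section 9.5 analyses permeability only as percent change per year, without adjusting for baseline Ki; modelling follow-up Ki on baseline Ki would be safer and needs no new data

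*Combined protocol and SAP*

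**What the plan says.** Section 9.5 says that for the secondary aims "each of the other outcomes will be analyzed with a similar approach" to that used for QSM. For permeability, a linear mixed model adjusted for gender "will be used to evaluate the difference in percent change per year in lesional and WMF permeability". The same sentence opens by setting out to assess the difference in the level of permeability, but percent change is the only scale it specifies. It does not say which scan is the divisor in year 2. A later secondary model adjusts for baseline factors found to be associated with outcome; baseline Ki is not among the factors listed.

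On measurement, the Image Post-Processing part of section 6.5.3 says that Ki "is estimated as the slope of the Patlak plot created by the above equation", fitted voxel by voxel. White-matter values come from "regions of interest (ROI) covering 3.6 X 3.6 mm (16 pixels or approximately 12.9 mm" squared per region, on a 256 matrix). The DCEQP part of section 6.5.2 gives the acquisition as a 230 x 182 mm field of view with "slice thickness = 8 mm, matrix size = 96x61, SENSE factor = 2".

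**The concern.** A percent change divides by the subject's own earlier measurement. When that measurement is noisy, the ratio is skewed: a few subjects with a low divisor can dominate the arm mean and inflate its variance. The pilot standard deviation, event threshold and effect size that support the percent score in sections 2.2 and 9.3.1 concern QSM. Nothing comparable is given for Ki, which is a regression slope and, for white matter, is read from small regions.

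Permeability is the first secondary aim, and section 2.2 treats its response to statin as an open question. A null result produced by a fragile score could be misread as no drug effect.

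**Working it through.** **1. The plan's own figure.** The documents size only the QSM outcome. With SD 30, within-person correlation 0, difference 20 points, two-sided alpha 0.05 and power 0.90 (section 9.3.1), n per arm = 2 x (1.960 + 1.282)^2 x [30^2 x (1 + 0)/2] / 20^2 = 2 x 10.507 x 450 / 400 = 23.6, so 24 by the normal approximation. The noncentral t version gives 25, as stated, and 44 and 17 at 15 and 25 points. The plan's figure reproduces. There is no counterpart for Ki.

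**2. Acquired voxels per white-matter region.**
- Acquired voxel: (230/96) x (182/61) = 2.40 x 2.98 = 7.15 mm^2 in plane.
- Region: 12.9 mm^2, so 12.9/7.15 = 1.8 acquired voxels.
- A 256 matrix over 230 mm has pixels of 0.898 mm. A 4 x 4 block covers (4 x 0.898)^2 = 12.9 mm^2, so the 16 pixels belong to an interpolated grid.

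**3. What a noisy divisor does.** Simulation with 25 per arm, between-subject variation of 30% and additive scan error, with no true change in controls:

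| Error, % of mean Ki | Mean year-1 percent change in controls | SD of the score |
|---|---|---|
| 10 | about +1 | about 16 |
| 20 | about +6 | about 36 |
| 30 | about +13 | about 70 |
| 40 | about +17 | about 138 |

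For comparison, the SD assumed for QSM is 30.

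**4. Power of the candidate analyses.** All inputs here are assumptions: lognormal true Ki with SD 0.3, a 25% fall on drug present at both 12 and 24 months, two-sided 5% test, gender left out, and 32 per arm (which equals 40 x 0.80, taking both 10% losses projected in section 9.3.2). Y0, Y12 and Y24 are Ki at baseline, 12 and 24 months. Error is additive.

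| Analysis | 20% error | 30% error |
|---|---|---|
| Mean of Y12/Y0 - 1 and Y24/Y12 - 1 | 35% | 7% |
| Percent change, baseline as only divisor | 74-81% | 29-33% |
| (Y24 - Y0)/2, absolute, unadjusted | 92% | 63% |
| Mean of Y12 and Y24, adjusted for Y0 | 99% | 92% |

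In the second row the lower end is the two-year percent change halved, and the upper end is the average of the two changes from baseline. At 20% error, the first step (35% to 74-81%) is due to the year-2 divisor, the next (to 92%) to the percent scale, and the last (to 99%) to baseline adjustment and use of both follow-up scans.

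At 10% additive error the first and third rows give 99% and 100%. At 30% additive error the type I error of the first score is about 2.5%: conservative, not inflated.

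**5. Proportional error.** At 30% error the percent scores give 60% (re-based) to 82% (baseline divisor), the unadjusted absolute contrast about 65%, and the baseline-adjusted model 94%. At 20% the re-based percent score and the absolute contrast are level (95% and 94%), with 99% once baseline Ki is added to the absolute contrast.

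**6. A different effect shape.** With a 20% fall in each year, 25 per arm and additive error of 20% / 30%, the re-based percent score has 72% / 20% power and the baseline-adjusted model about 100% / 93%.

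**The case against.** Several stronger readings are tempting, and the documents do not support them.

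- *White-matter Ki rests on two voxels per subject.* The 1.8 voxels are per region. The plan speaks of regions in the plural ("WMF regions are chosen in brain devoid of CA lesions on any MR sequence") without a count, and calls the acquisition parameters prototypical. Averaging four regions with independent errors would halve a 30% error to 15%, where the baseline-divided score has up to about 98% power and the re-based score about 74%.
- *The plan's score has 35% power where an absolute scale has over 90%.* That contrast needs year 2 to be divided by the 12-month scan. Section 9.5 does not say so for permeability. It is inferred from the QSM pilot, whose subjects "underwent paired QSM assessments at the beginning and end of each person-year epoch". With baseline as the only divisor the gap is much smaller.
- *Ki is known to be too noisy, or goes negative.* No repeatability is reported, nor any zero or negative value. The error form is unknown too. In the Patlak equation, a scale error in the arterial input multiplies every Ki in a scan, so some error is probably proportional. In that case the percent scale itself loses little or nothing.
- *Percent change has no precedent for permeability.* Section 2.2 reports a mean change of +85.9% in lesional permeability for lesions that bled. The voxel count also says nothing about lesional Ki, whose region is drawn around the lesion.

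It is also fair to say that section 9.5 plans a review of distributions and reports medians and ranges. That would expose heavy tails, but it names no alternative analysis. What remains is that the one pre-specified analysis depends on an unknown error structure, while the baseline-adjusted model did as well or better in every case run.

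**Conclusion.** The point holds as a low-cost improvement to a secondary analysis. Percent change is the only permeability scale specified, its pilot support is for QSM, and baseline Ki is not in the model. How much power this costs cannot be read from the documents. Under the stated assumptions the cost is negligible at 10% error. With additive error it is material from about 20%: 35% or 74-81% power, depending on the divisor, against 99% for the adjusted model. With proportional error the gain is mainly from baseline adjustment (94% against 60-82% at 30% error). None of this shows that the planned analysis will miss an effect, and it does not touch the primary QSM outcome or the sample size.

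**What to change.** In section 9.5, make the permeability analysis a linear mixed model of follow-up Ki at 12 and 24 months, with treatment, visit, baseline Ki and gender. Use absolute Ki for white matter, and absolute or log Ki for the lesion, chosen before unblinding. If a percent is wanted, express the treatment effect as a percent of the placebo mean. Keep individual percent changes as description, and state their divisor. It would also help to state how many white-matter regions are taken per subject, how they are combined, and any Ki repeatability already in hand.

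The cost is SAP wording. The effect becomes an average difference in Ki over the two follow-up visits, not a yearly rate, and the text should say so. No new data, visits or scans are needed.
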